9.1.3.11. PROMIS Itch Questionnaire Mood and Sleep Short Form 8a v1.0

The Mood and Sleep Short Form 8a (PIQ – Mood and Sleep) within the PROMIS Itch item bank consists of 8 items assessing mood and sleep related quality of life impairment from itch and impact of itch “in the past 7 days”. Response options range from 1=Never, 2=Rarely; 3=Sometimes; 4=Often; to 5=Almost always; total raw scores are converted to T-Scores with higher scores representing greater impact on mood and sleep because of itch.

9.1.3.12. PROMIS Itch Questionnaire Scratching Behavior Short Form 5a v1.0

The Scratching Behavior Short Form 5a (PIQ – Scratching Behavior) within the PROMIS Itch item bank consists of 5 items assessing quality of life impairment from scratching behavior and the physical manifestations of itch in adults “in the past 7 days”. Response options for the frequency of scratching behaviors range from 1=Never, 2=Rarely, 3=Sometimes; 4=Often, to 5=Almost always. The response options for the worry related to scratching items range from 1=Not at all; 2=A little bit; 3=Somewhat; 4=Quite a bit; to 5=Very much. Total raw scores are converted to T-Scores with higher scores representing more scratching behavior.

9.1.3.13. PROMIS Sleep Related Impairment Short Form 8a v1.0

The Sleep Related Impairment Short Form 8a (PROMIS – Sleep Impairment [PROMIS 2015]) within the PROMIS bank consists of 8 items measuring self-reported perceptions of alertness, sleepiness, and tiredness during usual waking hours, and the perceived functional impairments during wakefulness associated with sleep problems or impaired alertness “in the past 7 days”. Response options range from 1=Not at all; 2=A little bit; 3=Somewhat; 4=Quite a bit; to 5=Very much. Total raw scores are converted to T-Scores with higher scores representing greater sleep impairment.

9.1.3.14. Neuro-QoL Cognitive Function Short Form v2.0

Neuro-QoL is a set of self-reported measures that assess the health-related quality of life (HRQOL) of adults and children with neurological disorders and is comprised of item banks and scales that evaluate symptoms, concerns, and issues that are relevant across disorders along with instruments that assess areas most relevant for specific patient populations (NINDS 2015). The Cognitive Function Short Form v2.0 (Neuro-QoL – Cognitive Function) domain within Neuro-QoL bank consists of 8 items measuring Executive Function (perceived difficulties in applications of mental health function related to planning, organizing, calculating, remembering and learning) “in the past 7 days” and General Concerns (perceived difficulties in everyday cognitive abilities such as memory, attention, and decision making) using the lead-in phrase

“how much difficulty do you currently have...”. The response options for the Executive Function items range from 1=Very Often (several times a day); 2=Often (once a day); 3=Sometimes (2-3 times); 4=Rarely (once); to 5=Never). The response options for the General Concerns items range from 1=Cannot do; 2=A lot; 3=Somewhat; 4=A little, to 5=None. The total raw scores are converted to T-Scores with higher scores indicating better (desirable) self-reported health.

9.1.3.15. Patient Benefit Index

The Patient Benefit Index (PBI) measures patient-defined treatment objectives and benefits, particularly in the course of a treatment (Augustin et al. 2009; Blome et al. 2011). It consists of 2 questionnaires. Before therapy, patients complete the standardized “Patient Needs Questionnaire” indicating individual importance of treatment objectives. This reflects their personal preferences with respect to therapeutic benefit. During the study, patients rate the extent to which the treatment objectives have been achieved in the “Patient Benefit Questionnaire”. Response options range from 0=not at all, 1=somewhat; 2=moderately; 3=quite; 4=very; to 5=does/did not apply to me. A global score is calculated for each patient by weighing the achievement values of the treatment objectives by their importance to the individual patient. Moreover, the PBI will be supplemented by 6 rating scales assessing the following areas: physical well-being, emotional well-being, performance capacity on the job and in everyday living, social contacts, leisure activities, and quality of life. Patients with $PBI \geq 1$ are considered having at least minimum patient-relevant treatment benefit.

9.1.4. Appropriateness of Assessments

All assessments utilized in this study are standard, widely used, and generally recognized as reliable, accurate, and relevant except ADSS and Skin Pain NRS, which are currently being developed and validated according to regulatory guidances.

9.2. Adverse Events

Investigators are responsible for monitoring the safety of patients who have entered this study and for alerting Lilly or its designee to any event that seems unusual, even if this event may be considered an unanticipated benefit to the patient.

The investigator is responsible for the appropriate medical care of patients during the study.

Investigators must document their review of each laboratory safety report.

The investigator remains responsible for following, through an appropriate health care option, AEs that are serious or otherwise medically important, considered related to the investigational product or the study, or that caused the patient to discontinue the investigational product before completing the study. The patient should be followed until the event resolves or stabilizes with appropriate diagnostic evaluation; for events that are not anticipated to resolve or stabilize, the patient should be followed until the treating physician (in consultation with the sponsor) determines that appropriate followup has been completed. The frequency of follow-up evaluations of the AE is left to the discretion of the investigator.

Lack of drug effect is not an AE in clinical studies, because the purpose of the clinical study is to establish treatment effect.

After the ICF is signed, study site personnel will record via eCRF the occurrence and nature of each patient's preexisting conditions. In addition, site personnel will record any change in the condition(s) and any new conditions as AEs.

Investigators should record the following via eCRF for each AE: time of onset, time of termination, severity, and their assessment of the potential relatedness of each AE to investigational product.

The investigator will interpret and document whether or not an AE has a reasonable possibility of being related to study treatment, study device, or a study procedure, taking into account the disease, concomitant treatment, or pathologies. A "reasonable possibility" means that there is a cause-and-effect relationship between the investigational product, study device, and/or study procedure and the AE. The investigator answers yes/no when making this assessment.

Planned surgeries and nonsurgical interventions should not be reported as AEs unless the underlying medical condition has worsened during the course of the study.

If a patient's investigational product is discontinued as a result of an AE, study site personnel must report this to Lilly or its designee via eCRF, clarifying if possible the circumstances leading to any dosage modifications, or discontinuations of treatment.

9.2.1. Serious Adverse Events

An SAE is any AE from this study that results in 1 of the following outcomes:

- death
- initial or prolonged inpatient hospitalization
- a life-threatening experience (i.e., immediate risk of dying)
- persistent or significant disability/incapacity
- congenital anomaly/birth defect
- important medical events that may not be immediately life threatening or result in death or hospitalization but may jeopardize the patient or may require intervention to prevent 1 of the other outcomes listed in the definition above. Examples of such medical events include allergic bronchospasm requiring intensive treatment in an emergency room or at home, blood dyscrasias or convulsions that do not result in inpatient hospitalization, or the development of drug dependency or drug abuse.

All AEs occurring after signing the ICF are recorded in the eCRF and assessed for serious criteria. The SAE reporting to the sponsor begins after the patient has signed the ICF and has received investigational product. However, if an SAE occurs after signing the ICF, but prior to receiving investigational product, the SAE should be reported to the sponsor as per SAE reporting requirements and timelines if it is considered reasonably possibly related to study procedure.

Study site personnel must alert Lilly or its designee of any SAE within 24 hours of investigator awareness of the event via a sponsor-approved method (e.g. investigator space portal, telephone, or fax). If alerts are issued via telephone, they are to be immediately followed with official notification on study-specific SAE forms. This 24-hour notification requirement refers to the initial SAE information and all follow-up SAE information. Patients with a serious hepatic AE should have additional data collected using the hepatic safety eCRF. Investigators can contact the sponsor via telephone at any time using the qualified medical personnel or Lilly affiliate medical contact details which are provided in the site study file.

Pregnancy (during maternal or paternal exposure to investigational product) does not meet the definition of an AE. However, to fulfill regulatory requirements, any pregnancy should be reported following the SAE process to collect data on the outcome for both mother and fetus.

Investigators are not obligated to actively seek AEs or SAEs in subjects once they have discontinued and/or completed the study (the patient summary CRF has been completed). However, if the investigator learns of any SAE, including a death, at any time after a subject has been discharged from the study, and he or she considers the event reasonably possibly related to the study treatment or study participation, the investigator must promptly notify Lilly.

9.2.1.1. Suspected Unexpected Serious Adverse Reactions

Suspected unexpected serious adverse reactions (SUSARs) are serious events that are not listed in the IB and that the investigator identifies as related to investigational product or procedure. United States 21 CFR 312.32 and European Union Clinical Trial Directive 2001/20/EC and the associated detailed guidances or national regulatory requirements in participating countries require the reporting of SUSARs. Lilly has procedures that will be followed for the recording and expedited reporting of SUSARs that are consistent with global regulations and the associated detailed guidances.

9.2.2. Adverse Events of Special Interest

Adverse events of special interest will include the following:

- infections (including TB, herpes zoster, or opportunistic infections)
- malignancies (except for successfully treated basal or squamous cell carcinoma)
- hepatic events (Section 9.4.9)
- major adverse cardiovascular events (MACE) (Section 9.4.10)
- thrombotic events (such as deep vein thrombosis [DVT] and pulmonary embolism)

Sites will provide details on these AEs as instructed on the eCRF and may be asked for additional description by Lilly.

9.2.3. Complaint Handling

Lilly collects product complaints on investigational products and drug delivery systems used in clinical studies to ensure the safety of study participants, monitor quality, and to facilitate process and product improvements.

Patients will be instructed to contact the investigator as soon as possible if he or she has a complaint or problem with the investigational product so that the situation can be assessed.

9.3. Treatment of Overdose

Refer to the IB.

9.4. Safety

Any clinically significant findings from ECG testing, physical examination, vital signs measurements, or laboratory measurements that result in a diagnosis and that occur after the patient receives the first dose of study treatment should be reported to Lilly or its designee as an AE via eCRF.

9.4.1. Electrocardiograms

A single 12-lead standard ECG will be obtained locally at Visit 1 and read by a qualified physician (the investigator or qualified designee) at the site to determine whether the patient meets entry criteria.

Electrocardiograms may be obtained at additional times, when deemed clinically necessary.

9.4.2. Vital Signs

For each patient, vital signs should be measured according to the Schedule of Activities (Section 2).

9.4.3. Physical Examination

For each patient, a complete physical examination (excluding pelvic and rectal examinations) will be performed at Visit 1 (Screening). A symptom-directed physical examination will be performed at other visits as specified in the Schedule of Activities (Section 2). A complete physical examination may be repeated at the investigator's discretion at any time a patient presents with physical complaints.

9.4.4. Laboratory Tests

For each patient, laboratory tests detailed in [Appendix 2](#) should be conducted according to the Schedule of Activities (Section 2). With the exception of laboratory test results that may unblind the study, Lilly or its designee will provide the investigator with the results of laboratory tests analyzed by a central vendor, if a central vendor is used for the clinical trial.

9.4.5. Columbia Suicide Severity Rating Scale

The C-SSRS captures the occurrence, severity, and frequency of suicidal ideation and/or behavior during the assessment period. The scale includes suggested questions to solicit the type of information needed to determine if suicidal ideation and/or behavior occurred. The C-SSRS is administered by an appropriately trained health care professional with at least 1 year of patient care/clinical experience. The tool was developed by the National Institute of Mental Health trial group for the purpose of being a counterpart to the Columbia Classification Algorithm of Suicide

Assessment categorization of suicidal events. For this study, the scale has been adapted (with permission from the scale authors) to include only the portion of the scale that captures the occurrence of the 11 preferred ideation and behavior categories.

The nonleading AE collection should occur prior to the collection of the C-SSRS. If a suicide-related event is discovered *during the C-SSRS*, but was not captured during the nonleading AE collection, sites should not change the AE form. If an event is serious or leads to discontinuation, this is an exception where the SAE and/or AE leading to discontinuation should be included on the AE form and the process for reporting SAEs should be followed.

9.4.6. Self-Harm and Follow-up Supplement Forms

Suicide-related events (behavior and/or ideations) will be assessed and evaluated at every visit with the administration of the C-SSRS and the Self-Harm Supplement Form. The Self-Harm Supplement Form is a single question to enter the number of suicidal behavior events, possible suicide behaviors, or nonsuicidal self-injurious behaviors. If the number of behavioral events is greater than 0, it will lead to the completion of the self-harm follow-up form. The self-harm follow-up form is a series of questions that provides a more detailed description of the behavior cases.

9.4.7. Chest x-ray and Tuberculosis Testing

A posterior–anterior view chest x-ray will be obtained locally at screening (Visit 1), unless results from a chest x-ray obtained within 6 months prior to the study are available. The chest x-ray will be reviewed by the investigator or his or her designee to exclude patients with active TB infection. In addition, patients will be tested at screening (Visit 1) for evidence of active or latent TB as described in the exclusion criteria, Section 6.2.

Investigators should follow local guidelines for monitoring patients for TB if a patient is at high risk for acquiring TB or reactivation of latent TB.

9.4.8. Hepatitis B Virus DNA Monitoring

Patients who are HBcAb positive and HBV DNA negative (undetectable) at Visit 1 will require measurement of HBV DNA at Week 16 (Visit 8) or early termination visit, regardless of their hepatitis B surface antibody (HBsAb) status.

The following actions should be taken in response to HBV DNA test results:

- If a single result is obtained with a value “below limit of quantitation,” the test should be repeated within approximately 2 weeks. If the repeat test result is “target not detected,” monitoring will resume for those patients enrolling in the long-term extension study, JAHN.
- If the patient has 2 or more test results with a value “below limit of quantitation” or a test result above the limit of quantitation, the patient will be permanently discontinued from investigational product (Section 8.1.2) and should be referred to a hepatology specialist.

9.4.9. Hepatic Safety Monitoring and Data Collection

If a study patient experiences elevated ALT ≥ 3 x ULN, ALP ≥ 2 x ULN, or elevated TBL ≥ 2 x ULN, liver testing ([Appendix 4](#)) should be repeated within 3 to 5 days including ALT, AST, ALP, TBL, direct bilirubin, gamma-glutamyl transferase, and creatine kinase to confirm the abnormality and to determine if it is increasing or decreasing. If the abnormality persists or worsens, clinical and laboratory monitoring should be initiated by the investigator and in consultation with the study medical monitor. Monitoring of ALT, AST, TBL, and ALP should continue until levels normalize or return to approximate baseline levels.

Discontinuation criteria of investigational products, either temporary interruption or permanent discontinuation, due to abnormal ALT, AST, TBL, or ALP, are detailed in [Section 8.1](#).

Additional safety data should be collected via the hepatic eCRF if 1 or more of the following conditions occur:

- elevation of serum ALT to ≥ 5 x ULN on 2 or more consecutive blood tests
- elevated serum TBL to ≥ 2 x ULN (except for cases of known Gilbert's syndrome)
- elevation of serum ALP to ≥ 2 x ULN on 2 or more consecutive blood tests
- patient discontinued from treatment due to a hepatic event or abnormality of liver tests
- hepatic event considered to be an SAE

See [Appendix 4](#) and [Appendix 5](#) for a description of hepatic laboratory values that warrant exclusion from the study, temporary or permanent discontinuation of investigational product, or additional safety collection via the hepatic eCRF.

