eGFR <40 mL/min/1.73 m ² (from serum creatinine) for patients with screening eGFR ≥ 60 mL/min/1.73 m ²	eGFR ≥ 50 mL/min/1.73 m ²
eGFR <30 mL/min/1.73 m ² (from serum creatinine) for patients with screening eGFR ≥ 40 to <60 mL/min/1.73 m ²	eGFR ≥ 40 mL/min/1.73 m ²
ALT or AST >5x ULN	ALT and AST return to <2x ULN, and IP is not considered to be the cause of enzyme elevation
Hemoglobin <8 g/dL (<80.0 g/L)	Hemoglobin ≥ 10 g/dL (≥ 100.0 g/L)
Symptomatic herpes zoster	All skin lesions have crusted and are resolving
Infection that, in the opinion of the investigator, merits the IP being interrupted	Resolution of infection
Clinical features of VTE (such as deep vein thrombosis or pulmonary embolism) are present ^a	After evaluation and institution of appropriate treatment of VTE ^b

Abbreviations: ALT = alanine aminotransferase; ANC = absolute neutrophil count; AST = aspartate aminotransferase; eGFR = estimated glomerular filtration rate; IP = investigational product; ULN = upper limit of normal; VTE = venous thromboembolic event; WBC = white blood cell.

- a Evaluate promptly and institute appropriate treatment. Upon evaluation if VTE is ruled out and no other temporary or permanent discontinuation criteria are met, then IP may be resumed.
- b After evaluation and institution of treatment if the investigator deems that the patient is still at significant risk, or if this would constitute a second VTE for the patient, then IP should be discontinued permanently.

Although temporary interruption of investigational product is not a requirement at times of increased potential risk of VTE (e.g., surgery, significant air travel, or other situations involving prolonged immobilization) we recommend following appropriate VTE prophylaxis guidelines to help manage the VTE risk under these circumstances.

For specific guidance on temporary interruption of investigational product after use of a prohibited medication, please refer to Section 7.7.3 (Prohibited Medications and Procedures).

Lastly, investigational product should be temporarily interrupted for suicidal ideation or any suicide-related behaviors as assessed by the following patient responses on the C-SSRS:

- A “yes” answer to Question 4 (Active Suicidal Ideation with Some Intent to Act, Without Specific Plan) **or**
- A “yes” answer to Question 5 (Active Suicidal Ideation with Specific Plan and Intent) on the “Suicidal Ideation” portion of the C-SSRS **or**

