8.1.2. Permanent Discontinuation from Investigational Product

Investigational product should be permanently discontinued if the patient requests to discontinue investigational product.

Discontinuation of the investigational product for abnormal liver tests should be considered by the investigator when a patient meets 1 of the following conditions after consultation with the Lilly-designated medical monitor:

- ALT or AST >8x ULN
- ALT or AST >5x ULN for more than 2 weeks
- ALT or AST >3x ULN and total bilirubin level (TBL) >2x ULN or international normalized ratio (INR) >1.5

- ALT or AST >3x ULN with the appearance of fatigue, nausea, vomiting, right upper-quadrant pain or tenderness, fever, and/or rash
- ALP >3x ULN
- ALP >2.5x ULN and TBL >2x ULN
- ALP >2.5x ULN with the appearance of fatigue, nausea, vomiting, right quadrant pain or tenderness, fever, and/or rash

NOTE: Patients who are discontinued from investigational product due to a hepatic event or liver test abnormality should have additional hepatic safety data collected via the hepatic safety eCRF.

Investigational product should be permanently discontinued if any of the following laboratory abnormalities are observed:

- white blood cell count <1000 cells/ μ L ($1.00 \times 10^3/\mu$ L or 1.00 GI/L)
- ANC <500 cells/ μ L ($0.50 \times 10^3/\mu$ L or 0.50 GI/L)
- lymphocyte count <200 cells/ μ L ($0.20 \times 10^3/\mu$ L or 0.20 GI/L)
- hemoglobin <6.5 g/dL (<65.0 g/L)

NOTE: Temporary interruption rules (Section 8.1.1) must be followed where applicable. For laboratory values that meet permanent discontinuation thresholds, investigational product should be discontinued. However, if in the opinion of the investigator the laboratory abnormality is due to intercurrent illness such as cholelithiasis or another identified factor, laboratory tests may be repeated. Only when the laboratory value meets resumption thresholds (Table JAIY.4) following the resolution of the intercurrent illness or other identified factor, may the investigator restart investigational product, after consultation with the Lilly-designated medical monitor.

In addition, patients will be discontinued from investigational product in the following circumstances:

- pregnancy
- malignancy (except for successfully treated basal or squamous cell skin carcinoma)
- hepatitis B virus DNA is detected with a value above limit of quantitation or 2 sequential tests return a value of below the limit of quantitation (Section 9.4.8)

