Appendix 4. Hepatic Monitoring Tests for Treatment-Emergent Abnormality

Selected tests may be obtained in the event of a treatment-emergent hepatic abnormality and may be required in follow-up with patients in consultation with the Lilly, its designee, or the clinical research physician.

Hepatic Monitoring Tests

Hepatic Hematology^a

Hemoglobin
Hematocrit
RBC
WBC
Neutrophils, segmented
Lymphocytes
Monocytes
Eosinophils
Basophils
Platelets

Hepatic Chemistry^a

Total bilirubin
Direct bilirubin
Alkaline phosphatase
ALT
AST
GGT
CPK

Haptoglobin^a

Hepatic Coagulation^a

Prothrombin Time
Prothrombin Time, INR

Hepatic Serologies^{a,b}

Hepatitis A antibody, total
Hepatitis A antibody, IgM
Hepatitis B surface antigen
Hepatitis B surface antibody
Hepatitis B Core antibody
Hepatitis C antibody
Hepatitis E antibody, IgG
Hepatitis E antibody, IgM

Anti-nuclear antibody^a

Alkaline Phosphatase Isoenzymes^a

Anti-smooth muscle antibody (or anti-actin antibody)^a

Abbreviations: ALT = alanine aminotransferase; AST = aspartate aminotransferase; CPK = creatinine phosphokinase; GGT = gamma-glutamyl transferase; Ig = immunoglobulin; INR = international normalized ratio; RBC = red blood cell; WBC = white blood cell.

^a Assayed by Lilly-designated or local laboratory.

^b Reflex/confirmation dependent on regulatory requirements and/or testing availability.

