Appendix 5. Liver Function Testing and Hepatic Safety Monitoring

Liver Function Testing and Hepatic Safety Monitoring

Analyte	Exclusion Criteria	Additional Hepatic Testing	Hepatic eCRF Reporting	Temporary Interruption of IP	Permanent Discontinuation of IP after Consultation with the Lilly-Designated Medical Monitor
Protocol Section	Section 6.2	Section 9.4.9	Section 9.4.9	Section 8.1.1	Section 8.1.2
ALT/AST	≥2x ULN	ALT ≥3x ULN	ALT ≥5x ULN on ≥2 consecutive tests	≥5x ULN	
 • >8x ULN • >5x ULN for >2 weeks • >3x ULN AND TBL >2x ULN or INR >1.5 • >3x ULN with symptoms^a
ALP	≥2x ULN	≥2x ULN	≥2x ULN on ≥2 consecutive tests	No applicable criteria	
 • >3x ULN • >2.5x ULN AND TBL >2x ULN • >2.5x ULN with symptoms^a
TBL	≥1.5x ULN	≥2x ULN	≥2x ULN (excluding Gilbert's syndrome)	No applicable criteria	
 • ALT or AST >3x ULN AND TBL >2x ULN • ALP >2.5x ULN AND TBL >2x ULN

Abbreviations: ALP = alkaline phosphatase; ALT = alanine aminotransferase; AST = aspartate aminotransferase; eCRF = electronic case report form; INR = international normalized ratio; IP = investigational product; TBL = total bilirubin level; ULN = upper level of normal.

^a Fatigue, nausea, vomiting, right upper-quadrant pain or tenderness, fever, and/or rash

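### AST does not trigger the 3-5 day confirmatory liver panel, so an isolated, asymptomatic AST of 3-5x ULN has no required recheck until the next scheduled chemistry, nominally 28 days later

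*Protocol*

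**What the plan says.** **Confirmatory testing.** Protocol Section 9.4.9 opens with "If a study patient experiences elevated ALT" at 3x ULN or more, then lists ALP and total bilirubin (TBL), each at 2x ULN or more. Any of the three calls for a repeat within 3 to 5 days of ALT, AST, ALP, TBL, direct bilirubin, GGT and creatine kinase. AST is in the repeat panel but not among its triggers.

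**Hepatic eCRF.** The aminotransferase trigger in the same section begins "elevation of serum ALT to" and sets 5x ULN on at least two consecutive tests. In Appendix 5 the row is headed ALT/AST, but its eCRF cell reads "ALT ≥5x ULN on ≥2 consecutive tests", and its additional-testing cell also names ALT alone.

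**Where AST counts equally.**
- Exclusion criterion [44] applies to either enzyme at 2x ULN or more.
- Table JAIY.4 holds the drug when either exceeds 5x ULN. Restart requires: "ALT and AST return to <2x ULN, and IP is not considered to be the cause of enzyme elevation".
- All four aminotransferase conditions in Section 8.1.2 apply to either enzyme, for example "ALT or AST >3x ULN and total bilirubin level (TBL) >2x ULN or international normalized ratio (INR) >1.5".
- SAP Section 6.15.5.1 tabulates AST at 3x, 5x and 10x ULN in the same way as ALT.

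**The concern.** AST can exclude a patient, hold the drug and prompt permanent discontinuation, yet a raised AST does not require the quick confirmation that a raised ALT does. The protocol gives no reason for the difference.

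The purpose of the 3-5 day repeat is to confirm the abnormality and show whether it is rising or falling. For a patient whose only abnormality is AST of 3-5x ULN, that question can go unanswered until the next routine blood draw while dosing continues. If the value were rising towards the 5x ULN hold threshold, no required test would show it sooner. The stake is timeliness of safety monitoring in a narrow group, not the efficacy inference.

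**Working it through.** **Step 1. Which rules does the case meet?** Take AST of 3-5x ULN with ALT below 3x, ALP below 2x, TBL below 2x ULN and no symptoms.

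| Rule | Threshold | Met? |
|---|---|---|
| Repeat panel, 9.4.9 and Appendix 5 | ALT ≥3x, ALP ≥2x or TBL ≥2x | No |
| Hepatic eCRF, laboratory triggers | ALT ≥5x twice, TBL ≥2x, or ALP ≥2x twice | No |
| Hold, Table JAIY.4 | ALT or AST above 5x | No |
| Stop consideration, 8.1.2 | either above 8x | No |
| Stop consideration, 8.1.2 | either above 5x beyond 2 weeks | No |
| Stop consideration, 8.1.2 | either above 3x, with TBL above 2x or INR above 1.5 | Not on bilirubin; INR is not a scheduled test |
| Stop consideration, 8.1.2 | either above 3x with symptoms | No |

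At exactly 5x ULN the hold differs between the two places: Table JAIY.4 requires a value above 5x, while Appendix 5 prints 5x or more. This does not affect the rest of the band.

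**Step 2. When is the next required chemistry?** The Schedule of Activities places on-treatment chemistry at Visits 2, 5, 6, 7 and 8 (Weeks 0, 4, 8, 12 and 16), with none at Visits 3 or 4. Day = 7 × week gives 0, 28, 56, 84 and 112, matching the printed days. Tolerances are ±2 days at Visit 5 and ±4 days at Visits 6 to 8; Visit 2 is day 0.

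Nominal gap = later day − earlier day. Range = nominal gap ± the sum of the two tolerances.

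| Interval | Nominal gap (days) | Sum of tolerances | Range (days) |
|---|---|---|---|
| V2 to V5 | 28 − 0 = 28 | 0 + 2 = 2 | 26-30 |
| V5 to V6 | 56 − 28 = 28 | 2 + 4 = 6 | 22-34 |
| V6 to V7 | 84 − 56 = 28 | 4 + 4 = 8 | 20-36 |
| V7 to V8 | 112 − 84 = 28 | 4 + 4 = 8 | 20-36 |

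**Step 3. Compare with the ALT rule.** The same elevation in ALT requires a repeat in 3 to 5 days. On the nominal schedule the required AST recheck therefore comes 28 − 5 = 23 to 28 − 3 = 25 days later.

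A finding at Visit 8 is left out. Treatment in this study has ended by then, and the next draw is Visit 801 or falls in the extension study.

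**Step 4. Does any other text require an earlier recheck?**
- Section 9.2: "Investigators must document their review of each laboratory safety report". This requires review, not a repeat.
- Appendix 2, footnote b, allows extra chemistry panels when the investigator sees a need.
- Appendix 4: "Selected tests may be obtained in the event of a treatment-emergent hepatic abnormality". This is permissive.
- Section 9.4.10 has the sponsor's physician monitoring safety data and trends, with no recheck date.
- The continued monitoring in Section 9.4.9, which does name AST, follows only after a triggered abnormality persists or worsens.

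None sets a date for AST.

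**The case against.** The strongest reply is that the ALT-only trigger looks deliberate. Section 9.4.9 and Appendix 5 agree, and within the ALT/AST row only the two cells at issue name a single enzyme. AST can come from muscle, and creatine phosphokinase elevation is already a special safety topic in SAP Section 6.15.5.5, so some AST triggers would be false alarms. An ALT-led trigger is defensible. However, the documents state no rationale, and they let AST alone hold the drug. The creatine kinase and GGT in the repeat panel would help separate muscle from liver, which favours a quick recheck.

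A second reply is that discretion is the protocol's general approach: Section 8.1.1 leaves retest timing to the investigator even for held abnormalities. A careful investigator would probably recheck a value above 3x ULN well before 28 days. That stands as a limit on how often the full wait would occur. It does not remove the difference, because the same discretion exists for ALT and the protocol still mandates 3 to 5 days there.

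Three stronger readings are tempting but not supported:
- **Extra drug exposure.** A reader might count the delay as additional doses. A stable value of 3-5x ULN continues dosing under either rule, because the hold starts only above 5x. Doses would be saved only if the recheck showed progression or another criterion was met, and the documents give no probability for that.
- **An unusable INR criterion.** A reader might infer that the missing AST trigger blocks assessment of INR above 1.5. "Prothrombin Time, INR" appears in Appendix 4, but INR is not among the tests Section 9.4.9 names for the repeat, and Appendix 4 is permissive. A raised ALT does not clearly require INR either, so adding AST would not clearly supply it.
- **The eCRF omission as a cause of the wait.** Its threshold is 5x ULN on two tests, so it cannot affect AST of 3-5x. Above that range, discontinuation for a hepatic cause or a hepatic SAE still brings in the form, and SAP Section 6.15.5.1 profiles any single AST of 5x ULN or more.

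**Conclusion.** The point holds as a narrow gap in required monitoring. For an isolated, asymptomatic AST of 3-5x ULN found at Visits 2 to 7, the next required chemistry is nominally 28 days away instead of 3 to 5. The range is 26-30 days from Visit 2, 22-34 from Visit 5, and 20-36 from Visits 6 and 7.

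These figures assume that visits are kept within their windows, that the investigator orders no earlier test, and that time runs from draw to draw; the documents give no laboratory turnaround. They also give no frequency for this pattern, so the number of patients affected cannot be estimated.

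Related cases are largely covered: bilirubin at 2x ULN or more triggers the panel itself, AST above 3x with symptoms is a stop-consideration condition, and AST above 5x holds the drug. No endpoint, alpha or power changes. Minor; worth making because it is cheap.

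**What to change.** In Section 9.4.9 and in the additional-testing cell of Appendix 5, let ALT or AST at 3x ULN or more trigger the repeat panel, keeping the 3-5 day interval. The required recheck for AST then matches that for ALT.

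As a separate and lesser consistency edit, let ALT or AST at 5x ULN or more on two consecutive tests trigger the hepatic eCRF, in both places. This does not change anything for AST of 3-5x ULN.

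The cost is wording in one section and two table cells, plus one added eCRF trigger. Amendment (a) already revised hepatic criteria in Section 8.1.2 and Appendix 5, so an edit of this kind has precedent. The downside is a few more repeat chemistries and forms, some for AST of non-hepatic origin.
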